#### 1.4.2 Primary Safety Endpoint

Primary safety endpoint is measured by the cumulative occurrence of all adverse events defined in Appendix II of the CIP.

#### 1.4.3 Secondary Efficacy and Safety Endpoints

- Quality of Life: measured by the EuroQoL-5D-5L Quality of Life (EQ-5D-5L QoL)
- Functional Status: measured by the Six Minute Walk Test (6MWT) and New York Heart Association (NYHA) Classification
- Reoperations: Frequency and reasons of all reoperations
- Rehospitalizations: Frequency and reasons of all rehospitalizations
- Device Malfunction: Frequency and consequences of malfunction

*This confidential document is the property of Abbott and shall not be reproduced, distributed, disclosed or used without the express written consent of Abbott.*

## Statistical Analysis Plan

*NOTE: This is a PMS and all primary and secondary endpoints are not powered.*

### 1.5 Randomization

This is a single arm PMS and no randomization will be implemented.

### 1.6 Blinding

This is a single arm PMS and no blinding will be implemented.

## 2.0 ANALYSIS CONSIDERATIONS

### 2.1 Analysis Populations

The analysis population is advanced heart failure patients of all genders with a HM3 implant. Patients must meet the PMS Inclusion/Exclusion criteria and provide written informed consent.

### 2.2 Statistical Methods

#### 2.2.1 Descriptive Statistics for Continuous Variables

For continuous variables (e.g., age, weight, BMI, etc.), results will be summarized with the numbers of observations, means, standard deviations, quartiles, minimums, maximums, and the 95% confidence intervals for the means or median as appropriate. Comparison between subgroups of patient, when specified, will be summarized with the difference of the means or medians, p-values and 95% confidence intervals.

#### 2.2.2 Descriptive Statistics for Categorical Variables

For categorical variables (e.g. gender, implant strategy, etc.), results will be summarized with counts, percentages and the exact 95% Clopper-Pearson or multinomial confidence intervals as appropriate. Comparison between subgroups of patient, when specified, will be summarized with the difference in percentage, p-values and 95% confidence interval.

#### 2.2.3 Primary Efficacy Endpoint

The primary efficacy endpoint will be assessed using the Kaplan-Meier Product-Limit method. Subjects without an outcome, as defined in section 1.4.1, will be censored at the time of an elective transplant, explant for recovery, withdraw from the trial, lost to follow-up or the end of the 24 months surveillance period; whichever occurs first. A competing outcome graph will also be presented.

#### 2.2.4 Primary Safety Endpoint

The primary safety endpoint is the occurrence of all adverse events defined in Appendix II of the CIP, which will be assessed by percent of subjects with the event and events per patient-year (EPPY). Comparison between subgroups of patient, when specified, will be presented as relative risk or relative rate, p-values and 95% confidence interval.

*This confidential document is the property of Abbott and shall not be reproduced, distributed, disclosed or used without the express written consent of Abbott.*

## Statistical Analysis Plan

The incidence of important adverse events such as Stroke or Gastrointestinal (GI) Bleeding, relative to the time it occurred will be presented as freedom from event by using the Kaplan-Meier Product-Limit method if required.

### 2.2.5 Secondary Endpoints

#### 2.2.5.1 Six-minute Walk Test

Subjects may not be able to walk due to heart failure, especially at baseline. Subjects unable to walk due to heart failure will receive a score of 0 meters. The 6-minute Walk test will be conducted at all follow-up visits and the overall mean, median, standard deviation, minimum and maximum by visits will be presented. Differences in walking distance between each visit and baseline will be calculated and assessed for improvements using Wilcoxon signed-rank test. In addition, box plots will be used to show changes in walking distance over time.

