6.5 Subject Outcomes

Subjects will be followed until the 24-month follow-up is completed or until they experience an outcome, whichever occurs first. Outcomes include death, heart transplantation, HM3 exchange or explant, and withdrawal from the PMS. Outcomes must be reported to the Sponsor through the EDC system immediately upon discovery of the event.

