#### 1.3 Clinical Investigation Design

This is a prospective, single arm PMS which will enroll approximately 30 patients that meet the PMS Inclusion/Exclusion criteria, from approximately 4 sites in Hong Kong and Taiwan.

The surveillance period for this PMS is 24 months and follow-up visits will occur at Baseline/ Enrollment, HM3 Implant, 1, 3, 6, 12 and 24 months. All subjects will be followed from enrollment through the end of the 24 months surveillance period or occurrence of an outcome, whichever is earlier. Outcomes include Transplant, Explant, Exchange, Withdrawn or Death.

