#### 2.2.5.2 NYHA

Subjects' NYHA Functional Status will be assessed and percent of subjects in each class will be presented for all follow-up visits. For comparison, patients will be grouped into NYHA Class I/II (No limitation and Slight limitation of physical activity) vs. NYHA Class III/IV (Marked limitation and Inability to carry out physical activities). McNemar's test will then be used to assess if there is an increase in proportion of Class I and II subjects at each visit comparing to the baseline. In addition, bar charts will be used to show changes in NYHA classification over time.

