#### 2.2.5.3 EQ-5D-5L QoL questionnaire

Subject's quality of life will be measured by the EQ-5D-5L QoL questionnaire at baseline and all visits after HM3 implant until the end of surveillance period. EQ-5D-5L QoL Visual Analog Scale (VAS) score at each visit will be presented as mean, median, standard deviation, minimum and maximum. Comparison to baseline by visits will be performed using Wilcoxon signed-rank test.

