### 2.8 Handling of Missing Data

Data collected outside of the study visit window will be excluded from the analysis. Except for 6-minute Walk Test stated above, missing data will not be imputed.

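### Walk distance, NYHA class and EQ-5D VAS by visit describe only subjects still on HM3 support; label them so and add one all-implanted table

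*SAP*

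**What the plan says.** SAP 2.2.5.1 to 2.2.5.3 set out three comparisons with baseline, repeated at each visit:

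- Walk distance: "Differences in walking distance between each visit and baseline will be calculated and assessed for improvements using Wilcoxon signed-rank test".
- NYHA: "McNemar's test will then be used to assess if there is an increase in proportion of Class I and II subjects at each visit".
- EQ-5D VAS: "Comparison to baseline by visits will be performed using Wilcoxon signed-rank test".

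Who contributes at a visit is fixed elsewhere. SAP 1.3 states: "All subjects will be followed from enrollment through the end of the 24 months surveillance period or occurrence of an outcome, whichever is earlier". Protocol 6.5 lists what ends follow-up: "Outcomes include death, heart transplantation, HM3 exchange or explant, and withdrawal from the PMS". SAP 2.8 excludes out-of-window data and adds: "Except for 6-minute Walk Test stated above, missing data will not be imputed".

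Two rules do give a poor score to a subject who is doing badly. For the walk test, "Subjects unable to walk due to heart failure will receive a score of 0 meters". The NYHA table in Protocol Appendix II puts any inotrope-dependent subject in Class IV after enrollment. Both apply to subjects who are still being followed. Under Protocol 8.2.3.1, a walk test missing for any other reason stays missing.

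Deaths and exits are shown in the primary efficacy analysis, by Kaplan-Meier and a competing outcomes graph (Protocol 8.2.1, SAP 2.2.3).

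**The concern.** Protocol 2.1 makes functional and clinical outcome in implanted patients the primary objective, and SAP 2.1 defines the analysis population as patients with an HM3 implant. The functional results will nevertheless rest on a denominator that shrinks from visit to visit. A subject who dies, or whose pump is exchanged for device failure, is removed from it and is not counted as failing to reach Class I/II.

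Neither document says that these results apply only while the subject is alive on support, and none of the planned tables puts the functional result over all implanted subjects. A 24-month NYHA percentage shown beside a baseline percentage can easily be taken as the effect of implantation. SAP 2.4 allows descriptive reports for regulatory or reimbursement use, where that reading could carry weight.

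**Working it through.** The plan states no figure for this point, so there is nothing to reproduce. About 30 subjects is an accrual estimate (Protocol 8.3, SAP 2.3). The inputs below are the two-year results cited in Protocol 1.1.1.

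| Source | Survival s | NYHA I/II, baseline | NYHA I/II, 2 years (p) | Mean 6MWT, m |
|---|---|---|---|---|
| MOMENTUM 3 | 79.0% | 0% | 80% | 136 to 323 |
| CE Mark trial | 74% | 32% | 82% | 239 to 347 |
| ELEVATE | 83.4% | not given | not given | 104 to 350 |

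**Subjects lost to death.** 30 × 0.74 = 22.2 and 30 × 0.834 = 25.0 alive at 24 months, so about 5 to 8 deaths. Transplants and other exits reduce the paired set further. The documents give no rate for them.

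**NYHA percentage.** Assume p has survivors as its denominator; the Protocol does not state the denominator. The share of the cohort alive and in Class I/II is s × p, and the gap is p × (1 − s).

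- MOMENTUM 3: 0.79 × 0.80 = 0.632, or 63%; gap 0.80 × 0.21 = 0.168, about 17 points.
- CE Mark trial: 0.74 × 0.82 = 0.607, or 61%; gap 0.82 × 0.26 = 0.213, about 21 points.

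**Mean scores.** A whole-cohort mean needs a value for death, and any such value is a convention. Purely to show direction, count a death as no change, so that the cohort gain is s × (follow-up − baseline):

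- MOMENTUM 3: 0.79 × 187 = 148 m, against 187 m.
- ELEVATE: 0.834 × 246 = 205 m, against 246 m.
- CE Mark trial: 0.74 × 108 = 80 m, against 108 m.

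The cited means may not come from the same subjects at both times.

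**McNemar's test.** Only discordant pairs count. Take 30 subjects and assume no survivor worsens.

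- MOMENTUM 3 inputs: 24 alive, 19 of them in I/II (0.80 × 24 = 19.2), none at baseline. That is 19 gains and 0 losses. Counting the 6 deaths as not I/II adds no discordant pair, because they began in III/IV. The p-value is unchanged.
- CE Mark inputs: 22 alive, 7 in I/II at baseline (0.32 × 22 = 7.0) and 18 at follow-up (0.82 × 22 = 18.0). That is 11 gains and 0 losses, exact p = 2 × 0.5^11 = 0.001. Of the 8 deaths, about 3 began in I/II (0.32 × 8 = 2.6), giving 11 gains and 3 losses: p = 2 × (1 + 14 + 91 + 364) / 2^14 = 0.057.

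The reported percentage is affected whenever there are deaths. McNemar's p is affected only if some subjects who die began in Class I/II.

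**The case against.** An analysis of subjects alive on support is a legitimate choice, and the plan already shows most of what is needed to interpret it. Death, debilitating stroke and device-failure exchange form the primary endpoint. The competing outcomes graph shows how many remain on support. SAP 2.2.1 and 2.2.2 already call for numbers of observations, counts and exact intervals. The endpoints are unpowered (note to SAP 1.4.3), SAP 2.6 defines no success criterion, and nothing in the text claims a whole-cohort functional benefit. All of this stands, and it is why the point is only an improvement. What remains is that the on-support restriction is not stated, reasons for absence by visit are not planned, and a competing outcomes graph carries no functional data.

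Four stronger readings are tempting, and the documents do not support them:

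- *Poor results are never imputed.* The 0 m rule and the inotrope Class IV rule count two very poor states on support. They do not reach deaths or device-failure exchanges.
- *The tests compare survivors with everyone's baseline.* The tests are paired and use each subject's own baseline. The remark fits only the descriptive by-visit summaries.
- *Everyone who leaves was doing badly.* Elective transplant and explant for recovery also end follow-up, and the primary analysis censors them as non-failures. Multiplying by the share still on support would wrongly count them as failures.
- *Deaths should be ranked worst in the signed-rank tests.* Every subject is alive at baseline and there is no comparator. Such a test would largely repeat the primary endpoint, and the ranking is a debatable convention.

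**Conclusion.** The point holds as a cheap improvement to reporting. The by-visit functional and quality-of-life results apply to subjects still followed on HM3 with usable data, and they would overstate benefit if carried over to the implanted cohort. For NYHA I/II, the Protocol's own cited figures put the difference at about 17 to 21 points at two years. That rests on assuming that the cited percentages are among survivors and that mortality here will resemble those studies. It is an illustration, since the actual gap depends on deaths and exits not yet seen. The planned paired tests are not invalid; they answer a narrower question than the objective, and the plan does not say so.

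**What to change.** In SAP 2.2.5.1 to 2.2.5.3:

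1. State that the planned summaries and tests describe subjects while alive on HM3 support, and keep them as they are.
2. Add one table by visit with all implanted subjects as denominator. Give the proportion alive on support and in NYHA I/II with an exact 95% confidence interval. Count deaths and device-failure exchanges as not I/II. Show elective transplant, recovery explant, other explant or exchange, withdrawal, and missing or out-of-window data as separate categories.
3. For walk distance and EQ-5D VAS, report at each visit the number analysed and the reason for each absence.

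The cost is one table and some added counts. Subject status and outcome are already collected (Protocol Tables 3 and 5), so no visit or form changes, and no new test is needed. The downside is that the all-implanted figure will look less favourable than the on-support one.

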#### 2.2.5.2 NYHA

Subjects' NYHA Functional Status will be assessed and percent of subjects in each class will be presented for all follow-up visits. For comparison, patients will be grouped into NYHA Class I/II (No limitation and Slight limitation of physical activity) vs. NYHA Class III/IV (Marked limitation and Inability to carry out physical activities). McNemar's test will then be used to assess if there is an increase in proportion of Class I and II subjects at each visit comparing to the baseline. In addition, bar charts will be used to show changes in NYHA classification over time.

#### 2.2.5.3 EQ-5D-5L QoL questionnaire

Subject's quality of life will be measured by the EQ-5D-5L QoL questionnaire at baseline and all visits after HM3 implant until the end of surveillance period. EQ-5D-5L QoL Visual Analog Scale (VAS) score at each visit will be presented as mean, median, standard deviation, minimum and maximum. Comparison to baseline by visits will be performed using Wilcoxon signed-rank test.

#### 2.2.5.4 Rehospitalization and Reoperation

Percent of patients with events and frequency of events will be reported by reasons of rehospitalization and reoperation. Freedom from rehospitalization and reoperation will be assessed using the Kaplan-Meier Product-Limit method when specified.

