8.2.3.4 Rehospitalization and Reoperation

Frequency and reason will be reported for rehospitalization and reoperation. Freedom from rehospitalization and reoperation will be assessed using the Kaplan-Meier product-limit method.

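### The secondary Kaplan-Meier curves have no rule for death, transplant, explant or exchange; censoring them by default would make 1 minus Kaplan-Meier overstate the proportion of patients with the event

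*SAP*

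**What the plan says.** Protocol 8.2.3.4 commits to the rehospitalization and reoperation curves without condition: "Freedom from rehospitalization and reoperation will be assessed using the Kaplan-Meier product-limit method". SAP 2.2.5.4 repeats this with a qualifier at the end: "Freedom from rehospitalization and reoperation will be assessed using the Kaplan-Meier Product-Limit method when specified". For adverse events such as stroke and GI bleeding, SAP 2.2.4 says the time course will be shown as "freedom from event by using the Kaplan-Meier Product-Limit method if required". No other time-to-event method is named for these events.

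Crude summaries are planned alongside. For rehospitalization and reoperation: "Percent of patients with events and frequency of events will be reported by reasons of rehospitalization and reoperation". For adverse events, SAP 2.2.4 plans an assessment "which will be assessed by percent of subjects with the event and events per patient-year (EPPY").

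The only written censoring rule belongs to the primary efficacy endpoint (Protocol 8.2.1, SAP 2.2.3). There, subjects without an endpoint event "will be censored at the time of an elective transplant, explant for recovery, withdraw from the trial, lost to follow-up", or at the end of the 24 months. SAP 2.2.3 adds: "A competing outcome graph will also be presented". Nothing equivalent is written for the secondary curves.

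Protocol 8.1 and SAP 1.3 end a subject's follow-up at death, transplant, exchange, explant or withdrawal, or at 24 months.

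**The concern.** A subject who dies can no longer be rehospitalized, reoperated on or bleed. A subject who is transplanted, or whose pump is removed, leaves observation. An analyst who is told only to draw a Kaplan-Meier curve for a single event type will, unless told otherwise, censor at these exits. Kaplan-Meier then treats those subjects as if they still carried the same future risk as subjects on support. Its complement estimates incidence in a setting where the exits do not happen, and that is higher than the proportion of patients who actually have the event.

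The gap matters more here than for the primary endpoint. In the primary endpoint death is itself an event, the censoring rule is written down, and a competing outcome display is planned. In the secondary curves death is a genuine competing event and neither safeguard is present.

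At stake is a descriptive figure. The report could show a percent of patients with the event and a Kaplan-Meier value that disagree, with no explanation, and a reader could take the higher one as the observed burden.

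**Working it through.** The plan states no figure for these curves, so there is nothing to reproduce. The question is how far 1 minus Kaplan-Meier would sit above the true cumulative incidence.

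**Inputs from the protocol**
- Two-year survival on the device: 83.4% (post-approval registry), 79.0% (randomized pivotal trial) and 74% (CE Mark trial), all in section 1.1.1.
- Two-year event percentages in the pivotal trial's HM3 arm: stroke 9.9%, any bleeding 43.7% (section 1.1.1 and Appendix IV). No GI bleeding rate is given, so any bleeding stands in for it.

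**Assumptions, not in the documents**
- Constant, independent hazards over T = 2 years.
- Two-year transplant probability t: 0% in the base case, then 10%, 20% and 40%.
- Rehospitalization incidence 60%, for illustration only.

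**Formulas**
- Exit hazard: c = −ln(S)/2 − ln(1 − t)/2, where S is two-year survival.
- True cumulative incidence: e/(e + c) × (1 − exp(−2(e + c))). This is set equal to the event percentage and solved for the event hazard e.
- Complement of Kaplan-Meier with exits censored: 1 − exp(−2e).

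**Worked case: bleeding 43.7%, S = 79.0%, death only**
1. c = −ln(0.79)/2 = 0.1179 per year.
2. e = 0.3311 per year. Check: 0.3311/0.4490 × (1 − exp(−0.8980)) = 0.7374 × 0.5926 = 0.437.
3. 1 − exp(−0.6622) = 0.484. The curve reads 48.4% against a true 43.7%, an excess of 4.7 points.

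**Excess with death as the only competing exit**

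| Event (true incidence) | S = 83.4% | S = 79.0% | S = 74% | Patients of 30 |
|---|---|---|---|---|
| Stroke, 9.9% | +0.9 | +1.2 | +1.5 | 0.3 to 0.5 |
| Any bleeding, 43.7% | +3.6 | +4.7 | +6.1 | 1.1 to 1.8 |
| Rehospitalization, 60% (assumed) | +4.6 | +6.0 | +7.6 | 1.4 to 2.3 |

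**Excess with assumed transplants added, S = 79.0%**

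| Event | t = 10% | t = 20% | t = 40% |
|---|---|---|---|
| Stroke | +1.7 | +2.4 | +4.0 |
| Any bleeding | +6.9 | +9.3 | +15.1 |
| Rehospitalization (assumed 60%) | +8.6 | +11.5 | +18.0 |

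Over all combinations of S and t the excess runs from 0.9 to 4.4 points for stroke, 3.6 to 16.4 for bleeding and 4.6 to 19.4 for rehospitalization.

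**Against sampling error.** The approximate 95% half-width at n = 30 is 1.96 × √(p(1 − p)/30): 10.7 points at 9.9%, 17.7 at 43.7% and 17.5 at 60%. Only rehospitalization with 40% transplants and survival of 79.0% or 74% (18.0 and 19.4 points) goes beyond it.

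**Sensitivity to timing.** Suppose half of the cumulative event hazard H falls in months 0 to 3 (0.25 years). The event hazards are then h1 = 0.5H/0.25 and h2 = 0.5H/1.75, and the true incidence is h1/(h1 + c) × (1 − exp(−0.25(h1 + c))) + exp(−0.25(h1 + c)) × h2/(h2 + c) × (1 − exp(−1.75(h2 + c))). For bleeding with S = 79.0% this gives H = 0.623, and 1 − exp(−0.623) = 46.4%, an excess of 2.7 points instead of 4.7. Early clustering therefore roughly halves the bias.

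**The case against.** The strongest reply has four parts.

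**The documents never say that death and transplant are censored in these curves.** This stands. A reader might infer that the plan prescribes such censoring, but it is only the default that follows from the named method and the end-of-follow-up rule. Death could instead be counted as a failure, which would give event-free survival. The defect is that the handling is unstated.

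**The curves are optional and secondary.** This is true of the SAP, and no SAP section says when one is specified or required. It is not true of Protocol 8.2.3.4, which is unconditional for rehospitalization and reoperation. The SAP itself notes that no endpoint is powered, and it defines no success criterion.

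**Event burden is reported by other means.** This also stands. A reader might infer that the study will misreport how many patients have these events. It will not: the crude percentages, event frequencies and events per patient-year do not carry this inflation. The plan also asks for freedom from event, not for its complement labelled as incidence. What remains is the risk of two unexplained, differing figures. The crude percentage has its own limit, because it is affected by withdrawal and incomplete follow-up.

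**The large magnitudes are assumed.** This stands as well. A reader might infer a distortion of 10 points or more, but that needs exit or rehospitalization rates that the documents do not give. The case built wholly on the pivotal trial's own stroke and survival figures, 9.9% with 79.0%, gives +1.2 points, about 0.4 of a patient in 30.

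None of this justifies leaving the handling undefined. The bias runs in one direction only, and avoiding it needs no new data.

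**Conclusion.** The point holds as a modest one. The secondary curves lack any rule for death, transplant, explant or exchange, and the default reading of the plan would make 1 minus Kaplan-Meier too high as a statement of how many patients have the event. The direction is certain whenever such exits occur before the event and are censored.

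From the documents' survival and event figures, with death alone competing and hazards constant, the size is about 1 point for stroke and about 4 to 6 points for an event as common as any bleeding. A larger effect depends on the transplant rate, which is unknown here. Transplant is a realistic exit, because Protocol 2.2.1 includes bridge to transplant among the indications. A smaller effect follows if events cluster early. At about 30 subjects the bias is mostly smaller than the confidence interval half-width. It affects the interpretation of a secondary display and leaves the primary efficacy analysis and the crude safety summaries untouched.

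**What to change.** In Protocol 8.2.3.4 and SAP 2.2.4 and 2.2.5.4, state that whenever these curves are produced, the reported estimate is the Aalen-Johansen cumulative incidence with 95% confidence intervals, and give each exit a role:

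- **Competing events:** death, transplant and explant on all curves, subject to the reoperation rule below; pump exchange on all curves except reoperation.
- **Reoperation curve:** exchange counts as an event, because Protocol 6.4.2 handles pump exchange under reoperations and Protocol 8.2.1 speaks of reoperation for pump replacement. Any explant that meets the plan's meaning of reoperation also counts as an event. Listing exchange as competing on this curve would remove true events and understate the endpoint.
- **Censoring:** only withdrawal, loss to follow-up and end of surveillance.

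The SAP should also replace its conditional wording with a statement of which curves will be produced, so that it agrees with the protocol on rehospitalization and reoperation. Kaplan-Meier may be kept alongside for comparison with earlier reports, labelled as treating exits as censored.

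The cost is wording in both documents and a little more analysis work. No new data are needed, since events and outcomes are already reported under Protocol 6.4 and 6.5.
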